## **LIST OF ABBREVIATIONS AND DEFINITION OF TERMS**

AIDS: Acquired Immunodeficiency Syndrome

HIV: Human Immunodeficiency Virus

## **ABSTRACT**

The overall goal of this 5-year Mentored Research Scientist Development K01-Award is to support [name], MPH become an independent investigator in the field of HIV prevention. The proposed project seeks to address the HIV crisis in Alabama, where rates of undiagnosed HIV in Black young men who have sex with men (18-29 years) exceed 20%. This project will adapt and test a behavioral intervention to promote HIV rapid testing in the community, deliver culturally appropriate prevention education, offer sociostructural supports, and refer eligible participants for pre-exposure prophylaxis. The proposed research study is to conduct a hybrid type 1 effectiveness-implementation pilot study of the adapted intervention in which the candidate will assess acceptability and feasibility of Kings (the adapted intervention). This rigorous project includes intensive training at the candidate's home university and from other prominent institutions; engagement within the Adolescent Medicine Trials Network for HIV/AIDS Interventions; comprehensive mentoring from senior HIV researchers with expertise in minority, youth, and men who have sex with men health; and a thoughtful research strategy that addresses significant threats, high rates of undiagnosed HIV and insufficient engagement with HIV prevention services, including pre-exposure prophylaxis, in Black young men who have sex with men in Alabama.

## **PROTOCOL**

The purpose of this study is to adapt and test Brothers Saving Brothers, a brief two-part intervention that has been shown to increase rates of HIV testing and acceptance of prevention education in Midwest Black young men who have sex with men but has not been adapted for the South. This will be accomplished by updating it for rapid testing, pre-exposure prophylaxis education, and to include structural supports. We will pilot-test the adapted intervention to estimate intervention effects.

Community Based Organization staff will facilitate the enrollment process. Potential participants will directly enter data into a virtual screener via Qualtrics. Data will be directly uploaded and stored on a secure, encrypted server. Inclusion criteria include age, identifying as Black, English speaking, resident of Alabama, being sexually active with men, identifying as male, and has not taken an HIV test in the prior 6 months. If eligible, the participant will be asked to provide informed consent. Informed consent will include the request to access medical records related to HIV re-testing and pre-exposure prophylaxis. Limited data on rates of pre-exposure prophylaxis exist, but since this study is with high-risk for HIV young men who have sex with men, we anticipate most participants will be eligible for pre-exposure prophylaxis per guidelines. After informed consent is collected, pre-study survey data will be self-reported. The system will then randomize participants to Kings or the standard control condition in a 2:1 allocation. Participants will be followed by 6-months post-enrollment.

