## **SAMPLE SIZE**

The original target sample size was N=60; however, this study ultimately enrolled N=59.

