## STATISTICAL POWER

As a pilot study, this project is not statistically powered.

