## STATISTICAL ANALYSIS PLAN

Descriptive statistics will be used to identify the characteristics of the sample. Baseline differences between the intervention group and control group will be examined using student's t tests (for continuous variables) or chi-square tests (for categorical variables). Second, the feasibility / acceptability / satisfaction will be evaluation through multiple indicators, with focus on the simple question, "I like this app."

Preliminary efficacy of the intervention will be assessed using both bivariate statistics (e.g., t test, chi-square test, and fisher exact test) and multivariate statistics adjusting for demographic factors and baseline differences. To examine the preliminary effect of the intervention, we compared changes over time in HIV knowledge, pre-exposure prophylaxis knowledge, internalized homophobia, everyday discrimination, and medical mistrust within each group, as well as the increase from baseline to 6-month between the two groups. We also will assess the differences in willingness to take HIV test, self-reported HIV testing rates, and interest in learning more about pre-exposure prophylaxis and pre-exposure prophylaxis consultation with prescription between the two groups using Chi-square and Fisher's exact test. The effect of the intervention will be further examined using a generalized estimating equation controlling for potential confounders including education, income and social support. All statistical analyses will be performed using the SAS 9.4 statistical software package.

Institutional Review Board  
**Protocol Oversight Review Form**Date Submitted to IRB: August 15, 2018Title of Project: Adapting and Pilot Testing a Behavioral Intervention to Incorporate Advances in HIV Prevention for Black Young MSM in AlabamaName of Principal Investigator: [name]

Signature of Principal Investigator: \_\_\_\_\_

School: Public HealthDepartment: Health Care Organization and PolicyDivision: NA

Review Process (as determined by Department Chair):

Departmental Review  
 Divisional Review (Division Director or Designate)  
 Center or Departmental Protocol Review Committee Review  
 Project Review Panel (PRP)—Appointed by the Department Chairman or Division Director (PRP report attached)

[figure not shown]
---

I have reviewed the proposed research and concluded that the following apply:

- The research is scientifically valid and is likely to answer the scientific question;

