#### 14. Purpose - in nontechnical, lay language

a. Summarize the purpose and objectives of this protocol in one short paragraph. **The purpose of this study is to adapt and test Brothers Saving Brothers (BSB), a brief two-part intervention that has been shown to increase rates of HIV testing and acceptance of prevention education in Midwest black YMSM, but has not been adapted for the South. This will be accomplished by updating it for rapid testing, PrEP education, and to include structural supports. I will pilot-test the adapted intervention to estimate intervention effects and document implementation contexts.**

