**b. Describe how outcomes will be measured for this protocol.** Community Based Organization (CBO) staff will facilitate the enrollment process. Potential participants will directly enter data into an iPad screener (via the iSurvey platform). For more information of the iSurvey platform, please visit <https://www.harvestyourdata.com/>. Data will be directly uploaded and stored on a secure, encrypted UAB server, that will be established through UAB Central IT with the assistance of the UAB School of Public Health IT team. The device will determine eligibility. Inclusion criteria include age, identifying as Black, English speaking, resident of AL, being sexually active with men, identifying as male (will include YTGW and those transitioning depending on Aim 1 results), and has not taken an HIV test in the prior 6-months. If eligible, the participant will be asked to provide informed consent. Informed consent will be written and require a physical signature. Informed consent will include the request to access medical records related to HIV re-testing and PrEP uptake. Limited data on rates of PrEP eligibility exist, but since this study is with high-risk for HIV YMSM, we anticipate most participants will be eligible for PrEP per guidelines. After informed consent is collected, pre-study survey data (see Table with tentative variables below; a full survey will be included via amendment in 2020, about 1 year before I begin to collect data from study participants) will be self-reported (the participant will enter his own responses on the device further ensuring confidentiality) on the same device. The system will then randomize participants to aBSB (N=30) or control (N=30). Block randomization will ensure a balance across intervention and control groups. Data collection will occur for 18 months: 12-months of recruitment followed by 6-months of follow-up.

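### The pilot's purpose is to estimate effects, but the analysis plan names significance tests and ties no comparison to an effect measure or confidence interval

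*Combined protocol and SAP*

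**What the plan says.** The PROTOCOL section states the aim: "We will pilot-test the adapted intervention to estimate intervention effects". Item 14.a of the IRB Human Subjects Protocol repeats it: "I will pilot-test the adapted intervention to estimate intervention effects and document implementation contexts". The STATISTICAL POWER section is one sentence: "As a pilot study, this project is not statistically powered".

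The STATISTICAL ANALYSIS PLAN section then says: "Preliminary efficacy of the intervention will be assessed using both bivariate statistics". The examples it gives are the t test, the chi-square test and Fisher's exact test. The same sentence adds multivariate analyses adjusted for demographic factors and baseline differences.

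- **Five scales** (HIV knowledge, PrEP knowledge, internalized homophobia, everyday discrimination, medical mistrust): changes are compared within each arm, and the increase from baseline to 6 months is compared between arms.
- **Four binary outcomes** (willingness to test, self-reported testing, interest in learning about PrEP, PrEP consultation with prescription): arms are compared by chi-square and Fisher tests.
- **GEE:** the effect is examined further in a model that controls for education, income and social support.

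The section names no risk difference, odds ratio, mean difference, confidence interval or precision target for any of these. It also states no alpha and no rule for declaring an effect.

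**The concern.** A test and an estimate answer different questions. A chi-square or Fisher p-value does not say how many more men tested or took up PrEP under Kings, or how uncertain that number is. A pilot that sets out to estimate effects should leave the next trial's designers with exactly that.

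The gap matters more because the trial is small. If p-values were the main output, a useful effect could easily pass as a null result. Under low power, an effect that did reach significance would tend to look larger than it is. Either result could mislead the planning of a larger trial.

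**Working it through.** The plan has no power or precision figure to reproduce, so the check asks what tests and intervals can each deliver at the enrolled size.

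**Inputs from the documents**
- Size: "The original target sample size was N=60; however, this study ultimately enrolled N=59".
- Allocation: "The system will then randomize participants to Kings or the standard control condition in a 2:1 allocation".

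**Assumptions, because the documents give no values**
- A split of 39 Kings v 20 control, which follows from 59 at 2:1.
- Two-sided alpha of 0.05.
- Control rates of 10% to 50%, differences of 10 to 40 points, and standardized differences d of 0.2, 0.5 and 0.8.
- No dropout, with 20% dropout (31 v 16) as a sensitivity case.

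**Step 1. Power for binary outcomes.** Every pair of binomial counts in 39 and 20 is listed, and the probabilities of the pairs with Fisher p ≤ 0.05 are summed. The half-width is 1.96 × √[p1(1−p1)/39 + p2(1−p2)/20].

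| Kings v control | Difference | Fisher power | 95% half-width |
|---|---|---|---|
| 30% v 20% | 10 points | 9% | ±23 points |
| 60% v 50% | 10 points | 9% | ±27 points |
| 60% v 40% | 20 points | 24% | ±26 points |
| 40% v 20% | 20 points | 27% | ±23 points |
| 70% v 50% | 20 points | 29% | ±26 points |
| 30% v 10% | 20 points | 35% | ±20 points |
| 50% v 20% | 30 points | 56% | ±24 points |
| 80% v 50% | 30 points | 62% | ±25 points |
| 60% v 20% | 40 points | 81% | ±23 points |
| 80% v 40% | 40 points | 85% | ±25 points |

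**Step 2. Power for scales.** The standard error of a mean difference is √(1/39 + 1/20) = 0.275 SD. The noncentrality is d/0.275, with 57 degrees of freedom. Power is 11% at d = 0.2, 43% at d = 0.5 and 82% at d = 0.8. The 95% half-width is 2.002 × 0.275 = 0.55 SD.

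**Step 3. How many of the nine outcomes would reach significance?** This is 5 × t-test power + 4 × Fisher power.
- Small effects (d = 0.2; 60% v 50%): 5 × 0.110 + 4 × 0.085 = 0.9.
- Moderate effects (d = 0.5; 70% v 50%): 5 × 0.432 + 4 × 0.290 = 3.3.
- Large effects (d = 0.8; 80% v 50%): 5 × 0.816 + 4 × 0.621 = 6.6.

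**Step 4. Size of a significant result.** With true rates of 60% v 40%, the probability-weighted mean difference over all outcomes with Fisher p ≤ 0.05 is 37 points, against a true 20.

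**Step 5. What an interval adds.** For rates of 60% v 40%, the Wald interval is 0.20 ± 1.96 × √(0.24/39 + 0.24/20) = 0.20 ± 0.264, or −6 to +46 points. The nearest attainable result below 60% is 23/39 v 8/20, a difference of 19 points. It has Fisher p = 0.18 and a Newcombe interval of −7 to +42 points. The p-value alone invites a null reading. The interval shows that the data fit anything from no effect to a large one.

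**Sensitivity.** With 20% dropout, power falls to 20% for 60% v 40%, 23% for 70% v 50% and 36% for d = 0.5. Half-widths grow to about ±22 to ±30 points and ±0.62 SD. Item 14.b of the IRB form plans 30 v 30 instead of 2:1. At 29 v 30, power is 30% for 70% v 50% and 47% for d = 0.5, so the conflict over allocation does not change the result.

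**The case against.** The documents do not support three stronger readings that a reader might infer.

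- **That efficacy is judged by significance tests alone.** The plan also includes adjusted analyses and a GEE, and a GEE yields a coefficient and a standard error. No alpha or success rule is stated, and the wording is of preliminary efficacy. The plan names tests rather than outputs, so it does not exclude reporting proportions and mean changes. This stands. It is equally true that the GEE is given no outcome, link, effect scale or interval, so nothing commits the investigators to reporting an estimate.
- **That most results will show no difference.** This depends on effect sizes that the documents do not give. Step 3 shows that it holds for small and moderate effects but fails for large ones, where about 6.6 of 9 tests would be significant. The within-arm comparisons were not evaluated.
- **That the purpose cannot be met.** The data and the planned model can produce the estimates. The plan leaves this open but does not prevent it. Estimation is also not the only aim: the abstract names acceptability and feasibility, and the plan provides for them.

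It is also fair to say that ±0.55 SD is an unadjusted figure. Baseline adjustment multiplies it by about √(1 − r²). With an assumed correlation r of 0.5 to 0.7, that gives 0.551 × 0.866 = 0.48 SD to 0.551 × 0.714 = 0.39 SD. Dropout works in the other direction.

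**Conclusion.** The concern holds as a mismatch between a stated purpose of estimation and an analysis plan that specifies tests without an effect measure or interval. The mismatch itself is plain from the text and rests on no assumption.

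Its size does rest on assumptions: a 39 v 20 split, two-sided alpha of 0.05, no dropout and the scenarios listed. Under these, p-values alone are uninformative for small to moderate effects. A true 20-point gain from 40% to 60% would be missed about three times in four and, when significant, would appear nearly twice its size on average. The plan does not secure its purpose, but it can still do so. The change should be made, but the omission does not invalidate the trial.

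**What to change.** Amend the STATISTICAL ANALYSIS PLAN section as follows.

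1. Report each of the four binary outcomes as the proportion in each arm and a risk difference with a Newcombe or Miettinen-Nurminen 95% interval.
2. Report each of the five scales as a between-arm mean difference at 6 months, adjusted for that scale's baseline value, with a 95% interval. This replaces the unadjusted comparison of increases.
3. For the GEE, name the outcomes and the effect scale, and report the treatment effect with its 95% interval.
4. State that conclusions about efficacy rest on the estimates and intervals, that p-values are descriptive, and that p > 0.05 will not be read as no effect.

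This needs no new data. Enrollment is complete, so the analysis and reporting are what can still be changed, and the amendment should be dated accordingly. The cost is some plan wording and a few output options. The downside is that the results will look less certain, with intervals of about ±20 to ±27 points, or about ±0.55 SD before baseline adjustment, and wider with dropout.

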## **DURATION**

This protocol will last about three years; each participant will be enrolled for six months after their enrollment.

## **SAMPLE SIZE**

The original target sample size was N=60; however, this study ultimately enrolled N=59.

## **INCLUSION OR POPULATION**

[figure not shown]
Age 18-29 years at the time of enrollment, identifying as Black, English speaking, resident of Alabama, sexually active with men, identifying as having sex = male, and has not taken an HIV test in the prior 6 months.

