**Inclusion Criteria for youth participants:**

- Youth aged 18 years, 0 months to 29 years, 11 months
- Identifies as Black (or African American)
- Identifies as biologically male
- Is sexually active with male partners (MSM)
- Hasn't taken an HIV test in 6-months
- Is not currently on PrEP
- English speaking
- Able and willing to provide informed consent

e. If participants will comprise more than one group or stratification, describe each group (e.g., treatment/intervention, placebo, controls, sham treatment) **and** provide the number of participants anticipated in each group. Data will be collected from black YMSM and outreach staff. For purposes of this study, black YMSM are 18-29 years, identify as black, and have sex with men (n=70). Staff include any CBO staff that engages with YMSM and conducts community-based HIV testing (n=30).

f. Indicate which, if any, of the special populations listed below will be involved in the protocol. Include the Special Populations Review Form (SPRF) if indicated.

Pregnant Women: Attach [SPRF—Pregnant Women, Fetuses, Neonates/Nonviable Neonates](#)

Fetuses: Attach [SPRF—Pregnant Women, Fetuses, Neonates/Nonviable Neonates](#)

Neonates/Nonviable Neonates: [SPRF—Pregnant Women, Fetuses, Neonates/Nonviable Neonates](#)

Prisoners: Attach [SPRF—Prisoners](#)

Minors (<18 years old): Attach [SPRF—Minors](#)

Employees or students at institution where research conducted

Persons who are temporarily decisionally impaired

Persons who are permanently decisionally impaired

Non-English Speakers

**For each box checked**, describe why the group is included **and** the additional protections provided to protect the rights and welfare of these participants who are vulnerable to coercion: Staff will inform the development and adaptation of the intervention, because of their personal experiences working with the local community. Staff are under no obligation to participate.

g. List any persons other than those directly involved in the protocol who will be at risk. If none, enter "None": None

h. Describe the recruitment process (e.g., medical record review, referrals, letter of invitation, existing patients) that will be used to seek potential participants (e.g., individuals, records, specimens).

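### Does the missing PrEP criterion in the population section undermine the comparison of PrEP prescription between arms?

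*Combined protocol and SAP*

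**What the plan says.** Eligibility for the young men is described five times in the combined protocol and SAP.

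- **Inclusion or Population:** age, race, language and residence, then "sexually active with men, identifying as having sex = male, and has not taken an HIV test in the prior 6 months". PrEP is not mentioned.
- **Protocol:** "Inclusion criteria include age, identifying as Black, English speaking, resident of Alabama, being sexually active with men, identifying as male", followed by the six-month HIV-test criterion. PrEP is not mentioned as a criterion.
- **IRB form, items 14.b and 17.a (Procedures for Aim 3):** essentially the same summary, again without a PrEP criterion.
- **IRB form, item 16.d (youth criteria):** a bulleted list that includes "Is not currently on PrEP".

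No visible list mentions HIV diagnosed before enrolment.

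The Statistical Analysis Plan compares "interest in learning more about pre-exposure prophylaxis and pre-exposure prophylaxis consultation with prescription between the two groups" by chi-square and Fisher's exact tests, and also plans "multivariate statistics adjusting for demographic factors and baseline differences". The Aim 3 procedures describe the PrEP outcome as whether the man began PrEP during the six months. Item 20.b says that men with a reactive study test do not receive the second part of the intervention and that their data from before the first part enter the analyses. The Sample Size section reports that "this study ultimately enrolled N=59".

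**The concern.** A man already taking PrEP, or already known to have HIV, has a PrEP outcome that the intervention can hardly alter. If such men were enrolled, they would pull the between-arm difference towards zero. If an existing prescription were also counted as a success, they would add noise. The protocol's stated purpose is "We will pilot-test the adapted intervention to estimate intervention effects", so a diluted estimate touches the aim of the study, and a reader cannot tell from the documents whether dilution occurred. The obvious responses would be to correct the population section and to add an analysis restricted to men who were not on PrEP and not known to be HIV-positive before randomisation.

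The HIV-testing comparison is scarcely exposed. All five descriptions require no HIV test in the previous six months, so only men already diagnosed could disturb it.

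**Working it through.** **Do the lists conflict?** Item 16.d is the form's formal answer on inclusion and exclusion, and it covers all youth participants. The Protocol section and items 14.b and 17.a introduce their criteria with open-ended wording. The population section reads as a plain list. The lists also differ on other points: item 16.d leaves out Alabama residence, and the population section leaves out ability and willingness to consent. Absence from one list is therefore weak evidence that a criterion was dropped, and no text admits PrEP users. Table 1 does not settle the matter. It names eight prescreening measures against a count of nine items, and item 14.b calls the variables tentative.

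**How much could it matter?** The plan has no figure to reproduce, because the Statistical Power section says the study is not powered. Assumed inputs:

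- New prescription among men at risk: 25% intervention, 10% control. Neither rate is in the documents.
- Arms of 39 and 20, from 59 × 2/3 = 39.3 and 59 × 1/3 = 19.7, using the 2:1 ratio in the Protocol section.
- q, the share whose outcome cannot respond: 0 to 20%, not in the documents. At q = 10% this is 59 × 0.10 = 5.9 men.
- No loss to follow-up.

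All-randomised difference = 15 × (1 − q) points: 15.0 at q = 0, 13.5 at q = 10%, 12.0 at q = 20%. The size of the difference does not depend on how existing users are coded.

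SE at q = 0: √(0.25×0.75/39 + 0.10×0.90/20) = 9.65 points. The loss is 1.5/9.65 = 0.16 SE at q = 10% and 3.0/9.65 = 0.31 SE at q = 20%.

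At q = 10%:

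| Analysis | Rates | Difference (points) | SE (points) | Difference/SE | Odds ratio |
|---|---|---|---|---|---|
| All randomised, existing users not counted | 22.5% vs 9.0% | 13.5 | 9.3 | 1.46 | 2.94 |
| All randomised, existing users counted | 32.5% vs 19.0% | 13.5 | 11.5 | 1.17 | 2.05 |
| Restricted to men at risk (35.1 vs 18) | 25% vs 10% | 15.0 | 10.2 | 1.47 | 3.00 |

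The SEs are:

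- not counted: √(0.225×0.775/39 + 0.09×0.91/20)
- counted: √(0.325×0.675/39 + 0.19×0.81/20)
- restricted: √(0.1875/35.1 + 0.09/18)

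At q = 20%, not counted gives 12.0/8.82 = 1.36, with SE √(0.20×0.80/39 + 0.08×0.92/20). Restricted gives 15.0/10.79 = 1.39, with SE √(0.1875/31.2 + 0.09/16).

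Item 14.b gives 30 per arm instead of 2:1. With 30 and 30, the q = 10% ratios are 13.5/9.24 = 1.46 and 15.0/10.14 = 1.48, so the allocation ratio does not drive the result.

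A second set of assumed rates (30% vs 10%, arms 39 and 20, two-sided 5% level) agrees. At q = 10%, approximate power is 34% with existing users not counted, 28% with them counted, and 35% restricted.

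**Which coding applies?** Under the Aim 3 description, a prescription held before enrolment is not a start within the six months. That is the not-counted row, where restriction raises the ratio by 0.01 at q = 10% and 0.03 at q = 20%, and the SE rises with it.

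**The case for a change.** The strongest reply is that the SAP wording is looser than the Aim 3 wording. Consultation with prescription could be read to include a prescription already held, and at q = 10% that coding alone moves the odds ratio from 2.94 to 2.05. Three of the five eligibility descriptions sit in the same IRB form, so successive versions do not fully explain the difference. Adjustment for baseline differences does not define a denominator, and the place of men with a reactive test in the PrEP comparison is left open. An unpowered pilot still owes its readers a defined estimate.

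Most of this is fair as a description of the text. The record would be clearer if it said which criterion the screener applied, how an existing prescription was coded and how reactive-test men were handled. What does not stand is the step from there to a change in the plan. The damaging case requires that PrEP users were enrolled and that their old prescriptions were counted as successes. The documents show neither, and the second fits poorly with the outcome described for Aim 3. That case also treats every affected man as a PrEP user, although men already diagnosed could not be counted as prescribed. A comparison between the two groups is ordinarily read as everyone randomised to them, and that comparison is valid for those enrolled. Restriction to men at risk answers a different question; it does not remove a bias.

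**Conclusion.** No change to the plan is needed. The five descriptions differ by omission, and the outcome in the SAP is described more loosely than in the Aim 3 procedures. Both are gaps in written detail that analysts can close from the screener and the baseline survey.

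On the assumed rates, the dilution is 1.5 to 3.0 points, or 0.16 to 0.31 of a standard error, for an affected share of 10 to 20%. It is nil if the screener applied the item 16.d criterion and no diagnosed man entered. With outcomes coded as the Aim 3 text describes, a restricted analysis gains almost nothing (1.46 against 1.47 at q = 10%) and widens the standard error from 9.3 to 10.2 points. It would also add a comparison to an unpowered pilot.

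Timing weighs against it too. Enrolment is complete, so editing a list cannot alter who entered. The SAP's past tense, "we compared changes over time in HIV knowledge", suggests that a subset added now could well be post hoc. It would also depend on baseline PrEP use having been recorded. These conclusions rest on assumed prescription rates, an unknown q, and no loss by six months.
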